#### **4.3.2.2 Confirmed objective response**

The primary efficacy analysis is based on the primary estimand 2 introduced in Section 1.2.1. It is defined according to the following attributes:

- The endpoint is confirmed objective response (confirmed CR or PR as BOR) as per RECIST 1.1.
- The treatment condition of interest is tusamitamab ravtansine in combination with ramucirumab.
- The analysis population is the subgroup of participants from the all-treated population (defined in [Section 3](#)) treated at the RP2D (ie, excluding participants treated at the starting dose if this differs from the RP2D).
- Intercurrent events:
  - The study intervention discontinuation intercurrent event will be handled with the treatment policy strategy. Confirmed objective response will be assessed based on tumor assessments regardless of study intervention discontinuation.
  - The further anticancer therapy (including further systemic anticancer therapies) intercurrent event will be handled with the “while not initiating further anticancer therapy” strategy. Confirmed objective response will be assessed based on tumor assessments done up to the time of initiation of further anticancer therapy.
- The population-level summary will include the ORR, defined as the rate of participants with confirmed objective response, and two-sided 95% confidence interval using the Clopper-Pearson method.

In the absence of confirmed objective response before the analysis cut-off date (taking into account the intercurrent event handling strategies), participants will be considered as non-responders, whatever the reason (including participants with non-evaluable best overall response).

#### **4.3.3 Sensitivity analysis**

No sensitivity analysis is planned in this study.

#### 4.3.4 Supplementary analyses

Number (%) of participants within each BOR category, including not evaluable as per RECIST 1.1 and reason for being not evaluable, will be provided on the subgroup of participants from the all-treated population treated at the RP2D (ie, excluding participants treated at the starting dose, if this differs from the RP2D).

As a supplementary analysis, confirmed objective response as per RECIST 1.1 will also be summarized on the subgroup of participants from the activity population (defined in Section 3) treated at the RP2D (ie, excluding participants treated at the starting dose if this differs from the RP2D). The same analytical approach as primary efficacy analysis defined in Section 4.3.2.2 will be used.

In addition, the best relative tumor change from baseline, defined as the smallest relative tumor change from baseline (where tumor change at time t is the difference between sum of the longest diameters of the target lesions at time t and baseline), will be summarized using a waterfall plot on the subgroup of participants from the all-treated population (defined in Section 3) treated at the RP2D (ie, excluding participants treated at the starting dose, if this differs from the RP2D).

#### 4.3.5 Subgroup analyses

To assess the homogeneity of the treatment effect across various subgroups, analyses will be performed on the primary efficacy endpoint (defined in [Section 4.3.1.2](#)) across the following subgroups (categories with fewer than 5 participants may be combined with other categories):

- Race (White, Other)
- Age group (<65,  $\geq$ 65 years)
- Sex (Male, Female)
- ECOG PS at baseline (0, 1)
- Smoking status (Never, Former and Current)
- PD-L1 expression (<1%,  $\geq$ 1% and <50%,  $\geq$ 50%)
- Circulating CEA at baseline (<100,  $\geq$ 100  $\mu$ g/L)
- Prior treatment with EGFR, ALK, or ROS1 inhibitors (Yes, No)
- Prior ICI treatment administration (Sequential, Combination with chemotherapy)
- Time from initial diagnosis (<12 months,  $\geq$ 12 months)
- Brain metastases (Yes, No)
- Number of organs involved (including primary tumor location) (<3,  $\geq$ 3)
- Tumor burden at baseline, ie, sum of the longest diameters of the target lesions (<100,  $\geq$ 100 mm)
- Prior taxanes (Yes, No)
- Prior antimicrotubules (including taxanes and vinca-alkaloids) (Yes, No)

Objective response rate estimate and the corresponding 95% confidence interval will be provided for each subgroup using the same method as applied to the primary analysis. Forest plots will be provided.

## 4.4 SECONDARY ENDPOINTS ANALYSIS

The secondary endpoints detailed in this section are the duration of response and the progression-free survival. Other secondary endpoints analyses are defined in Section 4.7 (AE, SAE, laboratory abnormalities) and Section 4.8 (PK, immunogenicity).

### 4.4.1 Key/Confirmatory secondary endpoint

No key/confirmatory secondary endpoint.

### 4.4.2 Supportive secondary endpoints

#### 4.4.2.1 *Definition of endpoints*

##### 4.4.2.1.1 *Duration of response*

DOR is defined as the time from the date of first initial occurrence of the confirmed CR or PR to the date of first documentation of objective progressive disease according to RECIST 1.1 (1, 2) or death due to any cause, whichever occurs first.

In the absence of disease progression or death, DOR will be censored at the date of the last evaluable tumor assessment (not showing documented disease progression) performed up to the date of initiation of new anti-cancer therapy.

##### 4.4.2.1.2 *Progression-free survival*

PFS is defined as the time from the date of the first administration of IMP to the date of the first documentation of objective progressive disease according to RECIST 1.1 (1, 2) or death due to any cause, whichever occurs first.

The analysis of PFS will be based on the following censoring rules:

- If documented disease progression or death is not observed prior to the initiation of a further anti-cancer therapy, then PFS will be censored at the date of the last evaluable tumor assessment performed up to the date of initiation of a further anti-cancer therapy.
- A participant without PFS event (documented disease progression or death) and without any evaluable post-baseline tumor assessment will be censored at the date of the first administration of IMP (Day 1).

#### **4.4.2.1.3 Disease control rate**

DCR will be estimated by dividing the number of participants with confirmed objective response or stable disease (CR or PR or SD as BOR), determined according to RECIST v1.1, by the number of participants from the analysis population.

#### **4.4.2.2 Main analytical approach**

##### **4.4.2.2.1 Duration of response**

Analysis of the DOR is based on an estimand defined according to the following attributes:

- The endpoint is duration of response.
- The treatment condition of interest is tusamitamab ravtansine in combination with ramucirumab.
- The analysis population is the subgroup of participants from the all-treated population (defined in [Section 3](#)) treated at the RP2D of tusamitamab ravtansine (ie, excluding participants treated at the starting dose, if this differs from the RP2D) and limited to participants who have achieved a confirmed objective response.
- Intercurrent events:
  - The study intervention discontinuation intercurrent event will be handled with the treatment policy strategy. DOR will be assessed based on tumor assessments regardless of study intervention discontinuation.
  - The further anticancer therapy (including further systemic anticancer therapies) intercurrent event will be handled with the hypothetical strategy. DOR will be assessed based on tumor assessments had a further anticancer therapy not being taken. DOR will be assessed based on tumor assessments up to the time of initiation of further anticancer therapy.
  - Two or more consecutive missing/unevaluable tumor assessments immediately before documented PD or death will be handled with the hypothetical strategy. DOR will be assessed based on tumor assessments had 2 consecutive tumor assessments not been missed immediately before documented PD or death. DOR will be assessed based on tumor assessments up to the last evaluable tumor assessment documenting no progression.
- The population-level summary will include the median DOR and associated 95% confidence interval using Kaplan-Meier methods.

In the absence of documented disease progression or death before the analysis cut-off date (taking into account the intercurrent event handling strategies), DOR will be censored at the date of the last evaluable tumor assessment (not showing documented disease progression) performed before the analysis cut-off date.

In the absence of confirmed objective response before the analysis cut-off date (taking into account the intercurrent event handling strategies), DOR will not be derived.

#### 4.4.2.2.2 Progression-free survival

Analysis of the PFS is based on an estimand defined according to the following attributes:

- The endpoint is progression-free survival.
- The treatment condition of interest is tusamitamab ravtansine in combination with ramucirumab.
- The analysis population is the subgroup of participants from the all-treated population (defined in [Section 3](#)) treated at the RP2D of tusamitamab ravtansine (ie, excluding participants treated at the starting dose if this differs from the RP2D).
- Intercurrent events:
  - The study intervention discontinuation intercurrent event will be handled with the treatment policy strategy. PFS will be assessed based on tumor assessments regardless of study intervention discontinuation.
  - The further anticancer therapy (including further systemic anticancer therapies) intercurrent event will be handled with the hypothetical strategy. PFS will be assessed based on tumor assessments had a further anticancer therapy not being taken. PFS will be assessed based on tumor assessments up to the time of initiation of further anticancer therapy.
  - Two or more consecutive missing/unevaluable tumor assessments immediately before documented PD or death will be handled with the hypothetical strategy. PFS will be assessed based on tumor assessments had 2 consecutive tumor assessments not been missed immediately before documented PD or death. PFS will be assessed based on tumor assessments up to the last evaluable tumor assessment documenting no progression.
- The population-level summary will include:
  - Kaplan-Meier estimates of the 25th, 50th and 75th percentiles and their associated 95% confidence intervals using a log-log transformation of the survival function and the method of Brookmeyer and Crowley.
  - Number (%) of participants at risk as well as the probabilities of being event-free at least at 2, 4, 6, 8, 10 and 12 months with 95% CIs using the Kaplan-Meier method and a log-log approach based on a normal approximation following the Greenwood's formula.
  - Kaplan-Meier curve including the number of participants at risk at key time points.

In addition, the number (%) of participants with an event and the type of event (documented disease progression or death without documented disease progression) and the number (%) of censored participants and reason for censoring (no baseline tumor assessment, no evaluable postbaseline tumor assessment, alive without documented disease progression, event occurred after two or more non-evaluable tumor assessments, or initiation of further anticancer therapy) will be analyzed.

In the absence of documented disease progression or death before the analysis cut-off date (taking into account the intercurrent event handling strategies), PFS will be censored at the

date of the last evaluable tumor assessment (not showing documented disease progression) performed before the analysis cut-off date, or at the date of the first administration of IMP (Day 1) if no baseline tumor assessment or no evaluable postbaseline tumor assessment has been done.

#### 4.4.2.2.3 *Disease control rate*

DCR analysis is based on an estimand defined according to the following attributes:

- The endpoint is disease control response (confirmed CR or PR or stable disease (SD) as BOR) as per RECIST 1.1.
- The treatment condition of interest is tusamitamab raptansine in combination with ramucirumab.
- The analysis population is the subgroup of participants from the all-treated population (defined in [Section 3](#)) treated at the RP2D of tusamitamab raptansine (ie, excluding participants treated at the starting dose if this differs from the RP2D).
- Intercurrent events:
  - The study intervention discontinuation will be handled with the treatment policy strategy. Confirmed objective response or stable disease will be assessed based on tumor assessments regardless of study intervention discontinuation.
  - The further anticancer therapy (defined as all further anti-cancer treatments and radiotherapies with curative intent) intercurrent event will be handled with the “while not initiating further anticancer therapy” strategy. Disease control response will be assessed based on tumor assessments done up to the initiation of further anticancer therapy.

The population-level summary will include the objective response rate, defined as the rate of participants with disease control response and 2-sided 95% confidence intervals using the Clopper-Pearson method.

In the absence of confirmed objective response and SD before the analysis cut-off date (taking into account the intercurrent event handling strategies), participants will be considered as non-DCR, whatever the reason (including participants with non-evaluable best overall response).

Disease control rate will also be summarized on the activity population as a supplementary analysis.

## 4.5 TERTIARY/EXPLORATORY ENDPOINTS ANALYSIS

Analyses of tertiary/exploratory endpoints (eg, biomarkers) are defined in [Section 4.8](#).

## 4.6 MULTIPLICITY ISSUES

No multiplicity issues are anticipated in this study.

## 4.7 OTHER SAFETY ANALYSES

All safety analyses will be performed on the all-treated population as defined in [Section 3](#), by dose level (if applicable) and overall, unless otherwise specified, using the following common rules:

- The analysis of the safety variables will be essentially descriptive, and no testing is planned.
- Safety data in participants who do not belong to the all-treated population (eg, treated but not enrolled) will be provided.

### 4.7.1 Extent of exposure

#### 4.7.1.1 Overall exposure

The dose information will be assessed by the following variables:

- Overall number of cycles started, defined by the number of cycles in which at least one dose of any study interventions is administered.
- Duration of IMP exposure (in weeks) is defined as (last day of exposure - first day of exposure + 1 day)/7.
  - The first day of exposure is defined as the first administration date with nonzero dose for at least 1 of the IMPs (tusamitamab ravidansine or ramucirumab).
  - The last day of exposure is the day before the theoretical date of the next administration (after the last administration), defined as the maximum between:
    - Last administration date + 14 days - 1 day for tusamitamab ravidansine,
    - Last administration date + 14 days - 1 day for ramucirumab.

The total number of cycles started, and the number of cycles started by participants, will be summarized as a quantitative variable and by category (number [%] of participants receiving at least 1 cycle, at least 2 cycles, etc). The duration of overall exposure will be summarized quantitatively.

The following variable will be computed to describe overall dose modification (cycle delay):

- Cycle delay: A cycle is deemed as delayed if the start date of the current cycle - 14 days - start date of the previous cycle is >2 days. Cycle delay is not defined for the first cycle.

Cycle delay will be analyzed at the participant (with number of participants used as denominator) and cycle (with number of cycles used as denominator) levels, as follows:

- Number (%) of participants with at least 1 cycle delayed
  - Number (%) of participants with a cycle delayed between 3 and 7 days (using maximum delay across all cycles)

- Number (%) of participants with a cycle delayed >7 days (using maximum delay across all cycles)
- Number (%) of cycles delayed
  - Number (%) of cycles delayed between 3 and 7 days
  - Number (%) of cycles delayed between 8 and 14 days
  - Number (%) of cycles delayed >14 days

#### **4.7.1.2 *Tusamitamab rfvrtansine exposure***

The dose information will be assessed by the following:

- Total number of cycles started.
- Number of cycles started per participant.
- Duration of tusamitamab rfvrtansine exposure (in weeks) is defined by (date of last administration of tusamitamab rfvrtansine + 14 days - date of first administration of tusamitamab rfvrtansine)/7.
- Actual dose (in mg/m^2). In case of dose interruption, actual dose will be the sum of the actual doses administered before and after the dose interruption.
- Cumulative dose (in mg/m^2): the cumulative dose is the sum of all actual doses of tusamitamab rfvrtansine, given from first to last administration.
- Actual dose intensity (ADI in mg/m^2/week): defined as the cumulative dose divided by the duration of tusamitamab rfvrtansine exposure (in weeks).
- Planned dose intensity (PDI in mg/m^2/week): corresponds to the planned dose multiplied by the theoretical total number of doses started and divided by the theoretical cycle duration expressed in weeks (ie, 2 weeks per cycle started).
- Relative dose intensity (RDI, in %):  $100 \times \frac{\text{ADI (mg/m}^2\text{/week)}}{\text{PDI (mg/m}^2\text{/week)}}$ .

The total number of cycles started, and the number of cycles started by participant will be summarized as a quantitative variable and by category (number [%] of participants receiving at least 1 cycle, at least 2 cycles, etc). Duration of tusamitamab rfvrtansine exposure, cumulative dose, ADI and RDI will be summarized quantitatively.

The following variables will be derived to describe dose modifications and dose interruptions:

- Dose reduction: The first administration will not be counted as a dose reduction. For the second and subsequent tusamitamab rfvrtansine administrations, dose reduction will be determined using the dose level intervals provided in [Table 6](#), by comparing the current dose level to the previous dose level. If the current dose level is below the dose level interval of the previous dose administration, then the current dose level is considered reduced.

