	Grade 3-4 Severe Eg, symptomatic bronchospasm, urticaria lesions covering $>30\%$ BSA, hypotension, angioedema.	Interrupt ramucirumab infusion and prematurely definitively discontinue ramucirumab	Interrupt tusamitamab rvtansine infusion and prematurely discontinue tusamitamab rvtansine and consider infusion delay.	Give diphenhydramine 50 mg IV and/or dexamethasone 10 mg IV and/or epinephrine and any required treatment per investigator judgement.
Ocular toxicity: Keratopathy/keratitis ^b associated with tusamitamab rvtansine	Grade 1 - Asymptomatic Corneal lesions only observed on routine ocular examination and not requiring topical treatment.	Administer ramucirumab at same dose, and same day as tusamitamab rvtansine	Next infusion of tusamitamab rvtansine at the same dose, with or without cycle delay, depending on the recommendation from the ophthalmologist (nature and extent of the lesion).	Standard ocular examination is planned as recommended by the ophthalmologist.
	Grade 2 Symptomatic or requiring topical treatment (curative) or limiting instrumental activity of daily life. Moderate decrease in visual acuity (best corrected visual acuity 20/40 and better or 3 lines or less decreased vision from known baseline)	Administer ramucirumab as planned, and re-introduce tusamitamab rvtansine when recovery to Grade 1	1 st episode: Omit tusamitamab rvtansine until resolution to Grade 1 (asymptomatic) and restart tusamitamab rvtansine at the same dose. 2 nd episode: Omit SAR until resolution to Grade 1 (asymptomatic) and tusamitamab rvtansine dose reduction. 3 rd episode: depending on benefit risk, premature definitive discontinuation of tusamitamab rvtansine may be envisaged	Standard ocular examination weekly until resolution ^{c, d} . Start curative treatment per ophthalmologist recommendation. After resuming study treatment, participant should be followed with standard ocular examination by every 2 cycles, even asymptomatic during next 4 cycles. If no recurrence, standard process with follow-up with ocular symptom is resumed. Management of study drug upon recurrence to be discussed according to Grade of the event at recurrence, clinical benefit from study drug and recommendation from the ophthalmologist.

Event	Symptoms severity (Nadir) (NCI CTCAE v5)	Management of IMP dosing (ramucirumab))	Management of IMP dosing (tusamitamab rvtansine)	Supportive care guidelines

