**Table 6 - Tusamitamab raptansine dose reduction criteria**

Actual dose level	Dose level interval
Starting dose (100 mg/m  )	>90 mg/m 
Dose level -1 (80 mg/m  )	>72.5 mg/m  and ≤90 mg/m 
Low dose	>0 mg/m  and ≤72.5 mg/m 

- Dose delay: A dose will be considered as delayed if the tusamitamab raptansine administration date of the current cycle - 14 days - tusamitamab raptansine administration date of the previous cycle is >2 days. Dose delay is not defined for the first cycle.
- Dose omission is defined as a dose not administered at the scheduled visit but administered afterwards.
- Dose interruption: a dose will be considered to be interrupted if the tusamitamab raptansine administration is stopped during an infusion regardless of whether it is restarted or not.

Dose modifications and dose interruptions will be analyzed by participant and cycle as follows:

- **Participant** (number of participants treated will be used as denominator)
  - Number (%) of participants with at least 1 dose modification
    - Number (%) of participants with at least 1 dose delayed
    - Number (%) of participants with at least 1 dose reduction
    - Number (%) of participants with at least 1 dose omission
    - Number (%) of participants with at least 1 dose interruption
- **Cycle** (number of cycles started will be used as denominator)
  - Number (%) of cycles with at least 1 dose modification
    - Number (%) of cycles with at least 1 dose delayed
    - Number (%) of cycles with at least 1 dose reduction
    - Number (%) of cycles with at least 1 dose omission
    - Number (%) of cycles with at least 1 dose interruption

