#### **4.7.1.3 Ramucirumab exposure**

The dose information will be assessed by the following:

- Total number of cycles started.
- Number of cycles started per participant.
- Duration of ramucirumab exposure (in weeks) is defined by (date of last administration of ramucirumab + 14 days - date of first administration of ramucirumab)/7.
- Actual dose (in mg/kg). In case of dose interruption, actual dose will be the sum of the actual doses administered before and after the dose interruption.

- Cumulative dose (in mg/kg): the cumulative dose is the sum of all actual doses of ramucirumab, given from first to last administration.
- Actual dose intensity (ADI in mg/kg/week): defined as the cumulative dose divided by the duration of ramucirumab exposure (in weeks).
- Planned dose intensity (PDI in mg/kg/week): corresponds to the planned dose multiplied by the theoretical total number of doses started and divided by the theoretical cycle duration expressed in weeks (ie, 2 weeks per cycle started).
- Relative dose intensity (RDI, in %):  $100 \times \frac{\text{ADI (mg/kg/week)}}{\text{PDI (mg/kg/week)}}$ .

The total number of cycles started, and the number of cycles started by participant will be summarized as a quantitative variable and by category (number [%] of participants receiving at least 1 cycle, at least 2 cycles, etc) Duration of ramucirumab exposure, cumulative dose, ADI and RDI will be summarized quantitatively.

The following variables will be derived to describe dose modifications and dose interruptions:

- Dose reduction: The first administration will not be counted as a dose reduction. For the second and subsequent ramucirumab administrations, dose reduction will be determined using the dose level intervals provided in [Table 7](#), by comparing the current dose level to the previous dose level. If the current dose level is below the dose level interval of the previous dose administration, then the current dose level is considered reduced.

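### Dose reduction is derived from the amount actually infused, compared only with the previous infusion, so a stopped infusion can count as a reduction and a prescribed reduction right after it can be missed

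*SAP*

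**What the plan says.** SAP 4.7.1.2 defines the actual dose as the amount given: "In case of dose interruption, actual dose will be the sum of the actual doses administered before and after the dose interruption". It then sets out dose reduction. "The first administration will not be counted as a dose reduction", but nothing stops the first administration from being the comparator for the second. From the second onward, "If the current dose level is below the dose level interval of the previous dose administration, then the current dose level is considered reduced".

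The intervals are in Table 6, whose first column is headed "Actual dose level". The bands are above 90 mg/m² (starting dose, 100), above 72.5 and up to 90 mg/m² (dose level -1, 80), and a Low dose band above 0 and up to 72.5 mg/m².

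SAP 4.7.1.3 uses the same test for ramucirumab, beginning "If the current dose level is below the dose level interval of the previous dose administration". Its Table 7 bands are above 7 mg/kg (8), above 5.5 and up to 7 (6), above 4 and up to 5.5 (5), and Low dose above 0 and up to 4.

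Dose interruption is a separate variable, met when the administration "is stopped during an infusion regardless of whether it is restarted or not". No rule removes an uncompleted infusion from the reduction flag, or from serving as the comparator for the next dose.

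The flag feeds the counts of participants and cycles with a reduction or any dose modification. It also feeds the exclusions of concentrations in SAP 4.8.1.1.3 and 4.8.1.3.

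**The concern.** A dose reduction is normally a decision to prescribe less. Here it is read off the delivered amount, so it also captures infusions that were prescribed in full and cut short. Protocol Section 10.4 (Appendix 4) foresees such infusions. For a Grade 3-4 infusion-related reaction the ramucirumab instruction is "Interrupt ramucirumab infusion and prematurely definitively discontinue ramucirumab". At a second or later infusion, that event can enter the table as a reduction although no lower dose was ever prescribed.

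The comparator creates the opposite error. Because only the previous infusion is consulted, a partial infusion lowers the reference, and a reduction prescribed for the next dose no longer falls below it. The derived count can therefore be too high or too low. At stake are the descriptive dose-modification tables for the combination and some of the PK exclusions.

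**Working it through.** The plan states no figure on this point, so there is none to reproduce. The check applies the rule as written to hypothetical dose sequences; these are not trial data.

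**Rule.** Administration *i* (*i* ≥ 2) is flagged if its actual dose is at or below the lower bound of the band holding the actual dose of administration *i* − 1.

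**Cut-offs for a false flag after a complete dose** (lower bound of the band ÷ planned dose):
- Tusamitamab ravtansine 100 mg/m²: 90/100 = 90%. Delivering 91% to 99% is not flagged.
- Tusamitamab ravtansine 80 mg/m²: 72.5/80 = 90.6%.
- Ramucirumab 8 mg/kg: 7/8 = 87.5%.
- Ramucirumab 6 mg/kg: 5.5/6 = 91.7%.

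**Sequences:**

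| Drug | Actual doses | Prescribed doses | Flagged by SAP rule | Flagged on prescribed dose |
|---|---|---|---|---|
| Tusamitamab | 100/50/100 | 100/100/100 | dose 2 | none |
| Tusamitamab | 100/95/80 | 100/100/80 | dose 3 | dose 3 |
| Tusamitamab | 100/50/80 | 100/100/80 | dose 2 | dose 3 |
| Tusamitamab | 50/80/80 | 100/80/80 | none | dose 2 |
| Tusamitamab | 100/80/70/80 | 100/80/80/80 | doses 2 and 3 | dose 2 |
| Ramucirumab | 8/5/8 | 8/8/8 | dose 2 | none |
| Ramucirumab | 8/5/6 | 8/8/6 | dose 2 | dose 3 |
| Ramucirumab | 5/6/6 | 8/6/6 | none | dose 2 |

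In 50/80/80 the first dose lies in the Low dose band. The 80 that follows is above that band, so it is not flagged, and the participant shows no reduction. In 100/50/80 the participant is counted once, which is right, but at the wrong cycle. An infusion interrupted and then completed has an actual dose of 100, so no error arises.

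**Size per participant.** Safety tables use the all-treated population, and SAP 1.1 expects about 30 to 36 treated participants: 1/36 = 2.8 points, 1/30 = 3.3 points.

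**PK.** SAP 4.8.1.1.3 and 4.8.1.3 exclude troughs after a reduction. After a partial infusion, exclusion of the next trough is appropriate, because exposure really was lower. In 50/80/80 the reduction to 80 is not flagged, so the troughs that follow it are not excluded on that ground.

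**The case against.** **The premise is partly inferred.** The operative sentence speaks of the current dose level and never states that this means the delivered amount, and the first two rows of Table 6 are nominal levels. The Low dose band does not settle it. Protocol Table 11 allows no second tusamitamab ravtansine reduction, while the text of Protocol 6.6.4 leaves a second reduction to case-by-case discussion (two statements that need reconciling). A prescribed dose in that band is therefore conceivable. What stands is that the term needs defining. The column heading and the definition of actual dose still make the delivered amount the natural reading, and a programmer following the text would produce the counts above.

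**The sequences are uncommon.** This stands. After a Grade 1-2 reaction Appendix 4 lets the infusion resume, and its footnote allows the remaining dose to be given. After Grade 3-4 the drug is discontinued, so there is normally no next dose to misclassify. A missed reduction needs an uncompleted infusion at or below the cut-off, a participant who continues, and a reduction prescribed for the very next dose.

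**Other tables separate the causes.** SAP Table 9 lists, by drug, adverse events leading to dose modification apart from those leading to interruption, and the corneal-event summary reports the action taken. A reader might infer that infusion reactions and toxicity-driven reductions cannot be told apart in the report. These tables do not support that.

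**A large distortion.** A reader might also infer that the reduction rate will be materially inflated. If 5% to 10% of 30 participants had one uncompleted infusion after the first, 1.5 to 3 false reductions would turn 5/30 (16.7%) into 6.5 to 8 of 30 (22% to 27%). Nothing in the documents supports that frequency. The sum also requires every such infusion to fall below the cut-off and none to occur in a participant with a true reduction.

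**Conclusion.** The rule as written gives wrong counts in identifiable cases, for both drugs. An uncompleted infusion after the first, delivering at or below the cut-off, is counted as a reduction that was never prescribed. A reduction prescribed for the next dose is not flagged, and if the partial infusion was the first, the participant can be lost from the count. This rests on reading the dose level as the delivered amount, which the text favours but does not state outright.

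The consequence is small. Each misclassified participant moves a descriptive rate by about 2.8 to 3.3 points, and the number of such participants is unknown and probably low. ORR, DLT incidence, cumulative dose and relative dose intensity do not use this flag and do not change. The documents do not support a claim that the tolerability conclusions or the PK summaries as a whole are compromised. Minor priority.

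**What to change.** In SAP 4.7.1.2 and 4.7.1.3, state that the Table 6 and Table 7 intervals are applied to the intended (prescribed) dose of each administration and compared with the intended dose at the previous administration. State that an infusion stopped early counts only as a dose interruption.

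This needs a matching PK change. SAP 4.8.1.1.3 and 4.8.1.3 exclude for reduction or delay, not for interruption, so the new definition alone would bring low-exposure troughs back into the summaries. Add to both sections that concentrations following an uncompleted infusion are also excluded from the descriptive statistics.

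The cost is a small change of SAP wording and programming for descriptive tables. No new data should be needed. The intended dose already underlies the 80% criterion and the 30% overdose rule in SAP Section 3, and Protocol 6.6.4 requires all changes to administration to be recorded in the eCRF. The eCRF fields themselves are not shown, so confirm that the intended dose is available at every cycle.
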